1.0 Objectives*

1.1 The purpose of our research is to compare the effectiveness of 40mg/ml sodium thiosulfate (STS) solution to normal saline (0.9% sodium chloride) when injected intralesionally for the treatment of calcinosis cutis. Our specific aim is to assess the response of dystrophic and idiopathic calcinosis cutis to the injections of sodium thiosulfate in our patients.

1.2 Our hypothesis is that three injections of STS, each spaced one month apart, will significantly improve our patients' calcinosis cutis condition to a point where they are effectively clear or have a 2-point improvement in their Physician Global Assessment (PGA) scores when compared to normal saline.

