8.0 Study Endpoints*

8.1 Study endpoints:

- Primary:
 - Change in size of study lesions
 - Change in Physician Global Assessment
 - Visual Analog Scale of pain of injection
- Secondary:
 - Adverse Events

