9.2 Timeline

- Subject visits
 - The sodium thiosulfate and saline solution will be prepared the same day as the subject's baseline visit after consent to participate is obtained.
 - Baseline Visit
 - Minute 00-15:
 - Informed consent, HIPAA authorization, and screening and enrollment process.
 - Minute 15-30:
 - Obtain demographics and medical history via Demographics Form and Medical History Form (attached)
 - Selection of 2 lesions of dystrophic or idiopathic calcinosis cutis.
 - Note: The lesions must be at least 2mm in diameter and no larger than 2cm in diameter. If a lesion smaller than 2cm is not available then a 2 cm x 2 cm portion of a larger lesions will be used.
 - One lesion will be "Lesion A", and the other will be "Lesion B" for the entire study duration.
 - Lesions will be labeled with their corresponding letter 'A' and 'B' with a marker and photographed
 - Assessment of calcinosis cutis lesions via Case Report Form (see attached).
 - Administration of STS and normal saline.
 - Minute 30-90:
 - Monitoring of subject for adverse events
- 48-hour follow-up phone call:
 - Minute 0-5:
 - Brief phone call to assess for any adverse reactions

A Comparative Study of the Efficacy of Intralesional Sodium Thiosulfate Versus Intralesional Normal Saline for the Treatment of Dystrophic and Idiopathic Calcinosis Cutis, A Double-Blind Randomized Placebo-Controlled Trial

-
- 1-month (+/- 8 days) Follow-up
 - Minute 00-30:
 - Lesions will be labeled with their corresponding letter 'A' and 'B' with a marker and photographed
 - Assessment of calcinosis cutis via Case Report Form (attached)
 - Administration of STS and normal saline.
 - Minute 30-90:
 - Monitoring of subject for adverse events
 - Debrief of subject
- 2-month (+/- 8 days) Follow-up
 - Minute 00-30:
 - Lesions will be labeled with their corresponding letter 'A' and 'B' with a marker and photographed
 - Assessment of calcinosis cutis via Case Report Form (attached)
 - Administration of STS and normal saline
 - Minute 30-90:
 - Monitoring of subject for adverse events
 - Debrief of subject
- 3-month (+/- 8 days) Follow-up
 - Minute 00-15:
 - Lesions will be labeled with their corresponding letter 'A' and 'B' with a marker and photographed
 - Assessment of calcinosis cutis via Case Report Form (attached)

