 - [name] will not be notified of the result until after completion of the study so as to keep him blinded.
 - The syringes will be labeled with an “A” or “B” label for blinding by [name], or [name].

- Administration of study solutions
 - A volume of 0.1 ml/cm² of normal saline or STS will be injected into each lesion. Therefore, a maximum of 0.4ml of 40mg/ml STS or 16mg of STS (given maximum size of 2 cm x 2 cm) will be used per visit per subject.
 - The same treatment lesion will be injected only with STS every injection and the same control lesion will be injected only with normal saline (0.9% sodium chloride) every injection. In other words, “Lesion A” will always be injected with solution A and “Lesion B” will always be injected with solution B.
 - [name], a board-certified dermatologist, will be administering all injections of STS and normal saline to minimize risks for subjects.

- Disposal Protocol:
 - After use, needles will be disposed of in red sharps container according to UCF Health policy
 - After use, urine samples will be disposed of in the toilet according to UCF Health policy

A Comparative Study of the Efficacy of Intralesional Sodium Thiosulfate Versus Intralesional Normal Saline for the Treatment of Dystrophic and Idiopathic Calcinosis Cutis, A Double-Blind Randomized Placebo-Controlled Trial

9.3 Risk Management:

- Subjects will be directly observed during the administration of the STS and normal saline for any adverse events. An anaphylaxis kit is available in clinic should any subject experience such an event. The principal investigator is certified in basic cardiopulmonary life support and an AED is present in the facility. Subjects will be provided with the phone number of the PI should any issues related to participation in the study arise.
- Sodium thiosulfate is currently FDA-approved for as an antidote in the treatment of cyanide poisoning. FDA phase III studies are currently being conducted for use in calciphylaxis.
- 0.9% Sodium chloride is currently FDA-approved for parenteral replenishment of fluid, diluting or dissolving drugs for intravenous, intramuscular or subcutaneous injection, according to instructions of the manufacturer of the drug to be administered.
- Sterile water is currently FDA-approved as a solvent or diluent vehicle for parenterally administered drugs or solutions and as a source of water for parenteral fluid replenishment after suitable additives are introduced.

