11.0 Data Management* and Confidentiality

11.1 Data will be reported descriptively [mean and standard deviation; median (min-max) and frequency and percentage]. Interrater reliability of PGA will be conducted using Cohen's kappa statistic. As a second step, differences across times and between groups will be explored with non-parametric tests, such as Kruskal-Wallis test and the Mann Whitney U test. Statistical significance will be tested at $p < .05$.

The data will be analyzed for significant differences with aid of a statistician. The results of the data analysis will be graphed for each parameter.

11.2 For our study, we will recruit up to 12 adult male and female volunteers ages 18 years and older. This number is estimated from clinical knowledge of the cases that present to treatment on an annual basis at the research site. Furthermore, a review of the existing literature suggests that the targeted sample size is commensurate to other published studies.^{3,4,13,5-12}

11.3 Data will be managed as follows:

- Data will be stored in the secure HIPAA-compliant database called REDCap.
- Unique identifiers will be created using sequential numbers (i.e. 1, 2, 4 etc.).
- No data collection instrument in REDCap will contain identifying information
- The Screening and Enrollment Log, Drug Accountability Log, Unblinded Treatment Document, Demographics Forms, Medical History Forms, Eligibility Forms Case Report Forms, Independent Observer Case Report Forms, Adverse

A Comparative Study of the Efficacy of Intralesional Sodium Thiosulfate Versus Intralesional Normal Saline for the Treatment of Dystrophic and Idiopathic Calcinosis Cutis, A Double-Blind Randomized Placebo-Controlled Trial

Event Forms (see attached documents) will all be stored in the regulatory binder in a locked drawer in a locked room at UCF Health. Only [name] will have access to this locked drawer.

- Photographs will be taken with a UCF Health digital camera. The photographs will then be transferred to a folder on a password protected HIPAA compliant network drive for clinical research at UCF Health. After transfer of photographs to clinical research folder they will be deleted from the camera. Photographs will be labeled with subject ID number and visits number (i.e Subject 01 3-month)

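### Three unranked primary endpoints have no fixed visit, rater or success rule, paired lesions are tested as independent groups, and the Section 1.2 success criterion is not a listed endpoint

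*Combined protocol and SAP*

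**What the plan says.** All references are to the combined protocol and SAP.

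- **Section 8.1** lists three primary endpoints: change in lesion size, change in PGA, and "Visual Analog Scale of pain of injection". Adverse events are the only secondary endpoint. No visit, rater, ranking or success rule is given.
- **Section 1.2** states the hypothesis. After "three injections of STS, each spaced one month apart", patients will be "effectively clear or have a 2-point improvement in their Physician Global Assessment (PGA) scores when compared to normal saline". This responder outcome does not appear in Section 8.1 or 11.1.
- **Section 11.1** starts with descriptive summaries. For the testing that follows, it says: "differences across times and between groups will be explored with non-parametric tests, such as Kruskal-Wallis test and the Mann Whitney U test". The sentence that begins "Statistical significance will be tested at" sets the threshold, p < .05. The section also says: "Interrater reliability of PGA will be conducted using Cohen's kappa statistic".
- **Section 9.2** fixes the pairing: "The same treatment lesion will be injected only with STS every injection and the same control lesion will be injected only with normal saline". Lesions are assessed at baseline and at 1, 2 and 3 months. Injections are listed at the first three of these visits. The "3-month (+/- 8 days) Follow-up" lists photographs and assessment but no injection. A blinded independent observer later completes a separate form from the photographs of each visit.
- **Section 4.1** plans 12 enrolled subjects to obtain 10 eligible ones. No power, effect size or variability is stated.

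**The concern.** The plan states a directional hypothesis, labels endpoints primary and sets a significance threshold, but does not say which single result would count as success. Several choices are left open:

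- which of size or PGA carries the efficacy claim;
- which of the three post-baseline visits is used. Section 1.2 implies Week 12, the only visit after all three injections, but Section 8.1 does not fix it;
- whose PGA is analysed. A kappa statistic implies at least two raters, and the supplied text uses them only for agreement;
- which test is used, since the named ones are introduced as examples.

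Efficacy could therefore be claimed from whichever combination falls below .05, while the Section 1.2 question gets no formal test. Injection pain is a tolerability measure and has no new value at Week 12. As a listed primary, a chance difference in pain could still be reported as a positive primary result.

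**Working it through.** The documents give no family-wise error rate or power, so there is no figure of theirs to reproduce.

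**Inputs.** The level is p < .05 (Section 11.1). Sidedness is not stated; two-sided is assumed, which puts 2.5% in the direction favouring STS. There are two efficacy endpoints, size and PGA (Section 8.1), three post-baseline visits at Weeks 4, 8 and 12 (Section 7.1), and 10 pairs (Section 4.1). Correlations are not given and are assumed below.

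**Independent, correctly sized tests.** The chance of at least one false result favouring STS among k tests is 1 - 0.975^k.

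| Tests counted | k | Chance favouring STS |
|---|---|---|
| One pre-specified test | 1 | 2.5% |
| Size and PGA, one visit, one rater | 2 | 1 - 0.975^2 = 4.9% |
| Size and PGA, three visits, one rater | 6 | 1 - 0.975^6 = 14.1% |
| Size, PGA and pain, once each | 3 | 1 - 0.975^3 = 7.3% |
| Size, PGA and pain, three times each | 9 | 1 - 0.975^9 = 20.4% |

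Pain has three values because there are three injections. Counting a second rater's PGA instead of pain also gives k = 3 and k = 9, so the same two figures. Repeated visits on the same lesions are not independent, so these are upper-end values.

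**Allowing for correlation.** Null simulation with size and PGA, one rater, 10 pairs, normal data and 20,000 trials per setting. The assumed (endpoint, visit) correlations were (0, 0), (0.3, 0.6) and (0.5, 0.7). Rates favouring STS:

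| Test | Lesion correlation | One visit | Three visits |
|---|---|---|---|
| Paired signed-rank | 0 to 0.5 | about 4-5% | about 10-14% |
| Mann-Whitney | 0 | about 4% | about 9-12% |
| Mann-Whitney | 0.3 | about 2% | about 4-6% |
| Mann-Whitney | 0.5 | about 1% | about 2-3% |

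Mann-Whitney falls because positive correlation r shrinks the variance of the STS-saline difference in proportion to 1 - r, while the test is calibrated for r = 0. Even the signed-rank rates are ceilings: with a coarse integer PGA, ties and zeros reduced the simulated two-sided size of one exact test to 1-3%.

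**Power of the Section 1.2 outcome by exact McNemar, 10 pairs, independent lesions, assumed response rates.**

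- Five discordant pairs all favouring STS give p = 2 × 0.5^5 = 0.0625; six give 2 × 0.5^6 = 0.031. At least six discordant pairs are therefore needed.
- 60% vs 10%: discordant probabilities 0.6 × 0.9 = 0.54 and 0.4 × 0.1 = 0.04; power 36.9%.
- 80% vs 10%: 0.8 × 0.9 = 0.72 and 0.2 × 0.1 = 0.02; power 78.2%.

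**The case against.** The best defence is that Section 11.1 is modest: it describes the data first, then explores differences with example tests in about 10 subjects. Section 1.2 already points to PGA after the third injection, and a pain difference could not support that hypothesis. The attached forms, which were not available, may define the PGA scale, the clear state and the rater's role. The named Mann-Whitney test may also be conservative enough to offset the multiplicity: at an assumed lesion correlation of 0.3 the one-visit rate is already below 2.5%, and at 0.5 the three-visit rate is close to it.

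Much of this stands, and it limits the size of the point. A reader might infer that the trial has a 14% or 20% false-positive rate. The documents do not support that. Those figures need independent, correctly sized tests and success on any one of them, and the plan states neither. Nor do the documents show an intention to select results; they only fail to rule it out.

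A reader might also infer that Section 1.2 should be rewritten around PGA change because a signed-rank test has more power. That is model-dependent. With an assumed latent-normal PGA change, signed-rank power at 60% vs 10% response is 70-98%. If lesions either improve by 2 points or do not change, all nonzero differences tie, the test becomes exact McNemar, and the advantage vanishes.

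What the defence does not answer is that a stated hypothesis, primary labels and a significance threshold invite a confirmatory reading. Conservatism from ignoring the pairing is accidental, depends on an unknown correlation, and disappears once a paired test is used, which the wording of Section 11.1 permits.

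**Conclusion.** The point holds as a failure of pre-specification. Three primaries are unranked, with no visit, rater or success rule. Multiplicity is not controlled, the named tests do not fit the paired design, and the hypothesis has no listed endpoint or test. The true error rate therefore differs from the stated level by an amount that the documents do not determine. For size and PGA it could reach about 4.9% at one visit and 14.1% over three, or lie below 2.5% at one visit if Mann-Whitney is used on moderately correlated lesions. These figures assume two-sided 5% tests, one rater and success on either endpoint; the simulated ones also assume the correlations shown. Confidence is high on the missing specification and low on the size of the error. This should be corrected before the data are analysed.

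**What to change.** In Section 8.1, name one primary efficacy endpoint based on PGA at Week 12, scored by one rater named in advance. Choose one of two routes:

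1. The Section 1.2 responder outcome by exact McNemar test. This keeps the hypothesis as written. The clear state should be tied to a PGA score if the attached forms do not already do so.
2. PGA change from baseline by exact signed-rank test, with a stated rule for ties and zeros, followed in fixed sequence by the responder outcome.

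In Section 11.1, replace the between-lesion Mann-Whitney test with the chosen paired test at two-sided 0.05. Make lesion size secondary, report injection-pain VAS as tolerability, and report Weeks 4 and 8 descriptively.

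**Cost.** No added visits, subjects or measurements. Stand-alone significance claims on size, pain and earlier visits are given up. Route 1 has the low McNemar power shown above; any gain from route 2 depends on the PGA distribution. If lesions are uncorrelated, pairing costs power: at an assumed 40% vs 10% response, under the latent-normal model, 34-46% for signed-rank against 50-54% for Mann-Whitney. At a lesion correlation of 0.5 it is 51-71% against 49-55%. If the photograph observer is the named rater, changes felt only by palpation may be missed.

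One limit remains. A single coin flip assigns A and B for all subjects (Section 9.2), so any test relies on the choice of lesions A and B being unrelated to prognosis.

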8.2 Primary and secondary safety endpoints

- Primary safety endpoints: Serious adverse event due to IL STS, will be required to withdraw.
- Secondary safety endpoints:

A Comparative Study of the Efficacy of Intralesional Sodium Thiosulfate Versus Intralesional Normal Saline for the Treatment of Dystrophic and Idiopathic Calcinosis Cutis, A Double-Blind Randomized Placebo-Controlled Trial

- Intolerance to pain associated with injections, will be required to withdraw.
- Vasovagal reaction. If a subject develops a vasovagal reaction, he or she will be given the option to withdraw but will not be required to withdraw.
- If a subject experiences a mild to moderate adverse event he or she will be given the option to withdraw but will not be required to withdraw.

9.0 Procedures Involved*

9.1 Our study is prospective double-blind randomized placebo-controlled trial that seeks to compare STS to a placebo saline when injected intralesionally for the treatment of dystrophic or idiopathic calcinosis cutis.

9.2 Timeline

- Subject visits
 - The sodium thiosulfate and saline solution will be prepared the same day as the subject's baseline visit after consent to participate is obtained.
 - Baseline Visit
 - Minute 00-15:
 - Informed consent, HIPAA authorization, and screening and enrollment process.
 - Minute 15-30:
 - Obtain demographics and medical history via Demographics Form and Medical History Form (attached)
 - Selection of 2 lesions of dystrophic or idiopathic calcinosis cutis.
 - Note: The lesions must be at least 2mm in diameter and no larger than 2cm in diameter. If a lesion smaller than 2cm is not available then a 2 cm x 2 cm portion of a larger lesions will be used.
 - One lesion will be "Lesion A", and the other will be "Lesion B" for the entire study duration.
 - Lesions will be labeled with their corresponding letter 'A' and 'B' with a marker and photographed
 - Assessment of calcinosis cutis lesions via Case Report Form (see attached).
 - Administration of STS and normal saline.
 - Minute 30-90:
 - Monitoring of subject for adverse events
- 48-hour follow-up phone call:
 - Minute 0-5:
 - Brief phone call to assess for any adverse reactions

A Comparative Study of the Efficacy of Intralesional Sodium Thiosulfate Versus Intralesional Normal Saline for the Treatment of Dystrophic and Idiopathic Calcinosis Cutis, A Double-Blind Randomized Placebo-Controlled Trial

-
- 1-month (+/- 8 days) Follow-up
 - Minute 00-30:
 - Lesions will be labeled with their corresponding letter 'A' and 'B' with a marker and photographed
 - Assessment of calcinosis cutis via Case Report Form (attached)
 - Administration of STS and normal saline.
 - Minute 30-90:
 - Monitoring of subject for adverse events
 - Debrief of subject
- 2-month (+/- 8 days) Follow-up
 - Minute 00-30:
 - Lesions will be labeled with their corresponding letter 'A' and 'B' with a marker and photographed
 - Assessment of calcinosis cutis via Case Report Form (attached)
 - Administration of STS and normal saline
 - Minute 30-90:
 - Monitoring of subject for adverse events
 - Debrief of subject
- 3-month (+/- 8 days) Follow-up
 - Minute 00-15:
 - Lesions will be labeled with their corresponding letter 'A' and 'B' with a marker and photographed
 - Assessment of calcinosis cutis via Case Report Form (attached)
- During each visit subjects will be monitored for any adverse events and asked about any potential adverse events since the last visit. Any adverse events will be logged on the Adverse Events Form (see attached).
- Visit 1 will be followed with a 48-hour post-treatment phone call to assess for any adverse events.
- After all subjects have completed their participation, photographs of lesions will be reviewed by [name] who will fill out the Independent Observer Case Report Form (see attached) for each visit. He will be blinded as to which lesions received which treatment and at which visit in the study the lesions were photographed.
- Screening and consent
 - First, each subject will sit down with the principal investigator to discuss the study in depth and review the screening criteria. After all risks, benefits, alternatives, and questions have been discussed consent will be obtained.
 - After the informed consent form is signed, the eligibility screening portion of the case report form will then be filled out by the principal investigator with the research subject. If necessary, a pregnancy test will be performed.

A Comparative Study of the Efficacy of Intralesional Sodium Thiosulfate Versus Intralesional Normal Saline for the Treatment of Dystrophic and Idiopathic Calcinosis Cutis, A Double-Blind Randomized Placebo-Controlled Trial

- Solution preparation
 - 50 ml vials of sodium thiosulfate (250mg/ml) will be used for preparation of the treatment solution.
 - The solution from the bottle will be diluted in a ratio of 1 part sodium thiosulfate 250mg/ml to 5.25 parts sterile water to yield a 40mg/ml solution of sodium thiosulfate.¹⁴ This is done to make the final solution as close to isotonic as possible.
 - 30 ml vials of sodium chloride 0.9% will be used for the control treatment.
 - The solutions will be drawn up in 1 cc syringes utilizing a 25g needle by [name]. The needle will then be replaced with a capped 30g ½ inch needle.
 - All solutions will be drawn up by [name] the day of use and discarded immediately after use.
 - Treatment and control will be randomized once for the entire study and all subjects based upon a one-time flip of a coin as follows:
 - If coin flip is heads: all “A” lesions will receive STS and all “B” lesions will receive normal saline
 - If coin flip is tails: all “A” lesions will receive normal saline and all “B” lesions will receive STS
 - This result will be recorded on the Unblinded Treatment Document (See attached).
 - [name] will not be notified of the result until after completion of the study so as to keep him blinded.
 - The syringes will be labeled with an “A” or “B” label for blinding by [name], or [name].

- Administration of study solutions
 - A volume of 0.1 ml/cm² of normal saline or STS will be injected into each lesion. Therefore, a maximum of 0.4ml of 40mg/ml STS or 16mg of STS (given maximum size of 2 cm x 2 cm) will be used per visit per subject.
 - The same treatment lesion will be injected only with STS every injection and the same control lesion will be injected only with normal saline (0.9% sodium chloride) every injection. In other words, “Lesion A” will always be injected with solution A and “Lesion B” will always be injected with solution B.
 - [name], a board-certified dermatologist, will be administering all injections of STS and normal saline to minimize risks for subjects.

- Disposal Protocol:
 - After use, needles will be disposed of in red sharps container according to UCF Health policy
 - After use, urine samples will be disposed of in the toilet according to UCF Health policy

A Comparative Study of the Efficacy of Intralesional Sodium Thiosulfate Versus Intralesional Normal Saline for the Treatment of Dystrophic and Idiopathic Calcinosis Cutis, A Double-Blind Randomized Placebo-Controlled Trial

9.3 Risk Management:

- Subjects will be directly observed during the administration of the STS and normal saline for any adverse events. An anaphylaxis kit is available in clinic should any subject experience such an event. The principal investigator is certified in basic cardiopulmonary life support and an AED is present in the facility. Subjects will be provided with the phone number of the PI should any issues related to participation in the study arise.
- Sodium thiosulfate is currently FDA-approved for as an antidote in the treatment of cyanide poisoning. FDA phase III studies are currently being conducted for use in calciphylaxis.
- 0.9% Sodium chloride is currently FDA-approved for parenteral replenishment of fluid, diluting or dissolving drugs for intravenous, intramuscular or subcutaneous injection, according to instructions of the manufacturer of the drug to be administered.
- Sterile water is currently FDA-approved as a solvent or diluent vehicle for parenterally administered drugs or solutions and as a source of water for parenteral fluid replenishment after suitable additives are introduced.
- The following are the source documents (see attached):
 - Subject ID Assignment Log
 - Screening and Enrollment Log
 - Drug Accountability Log
 - Unblinded Treatment Document
 - Eligibility Form
 - Demographics Form
 - Medical History Form
 - Case Report Form
 - Independent Observer Case Report Form
 - Adverse Event Form
 - Photographs of study lesions
- Details regarding the storage of the above information is outlined in Section 11.3.

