3.2 Screening Criteria

- Inclusion Criteria:
 - Male or female adult 18 years of age or older
 - Must have health insurance will be eligible to participate
 - Must have a current diagnosis of dystrophic or idiopathic calcinosis cutis
 - Subjects must have at least 2 lesions of at least 2mm in size

- Exclusion Criteria:
 - Unable to read and speak English
 - Allergy to any component of the sodium thiosulfate solution
 - Adults unable to consent
 - Individuals who are not yet adults (infants, children, teenagers)
 - Pregnant women
 - Women who are breastfeeding
 - Prisoners

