9.4 Data to be collected

- Age
- Gender
- Race
- Ethnicity
- Medical History
 - Past Medical and Surgical History
 - Medications

A Comparative Study of the Efficacy of Intralesional Sodium Thiosulfate Versus Intralesional Normal Saline for the Treatment of Dystrophic and Idiopathic Calcinosis Cutis, A Double-Blind Randomized Placebo-Controlled Trial

- Allergies
- Social History
 - Tobacco use
 - Alcohol use
- Laboratory Results
- Size of lesions
- Visual Analog Scale for Pain (VAS Pain)
- Physician Global Assessment (PGA)
- Photographs will also be taken of all study lesions during every assessment and will be stored directly in the password protected HIPAA compliant network drive for clinical research at UCF Health. Though the photos will not contain any identifiers, subjects are potentially identifiable from the photos and thus they will be stored in the password protected HIPAA compliant network drive for clinical research at UCF Health.

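### Lesions A and B need not be alike in body site, site is not a listed data item, and no pre-injection pain score is described, leaving the injection-pain contrast exposed to site differences

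*Combined protocol and SAP*

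**What the plan says.** Section 3.2 sets the lesion requirement for entry: "Subjects must have at least 2 lesions of at least 2mm in size". At the baseline visit, section 9.2 provides for "Selection of 2 lesions of dystrophic or idiopathic calcinosis cutis" and adds a size window: "The lesions must be at least 2mm in diameter and no larger than 2cm in diameter". There is a fallback for large lesions: "If a lesion smaller than 2cm is not available then a 2 cm x 2 cm portion of a larger lesions will be used". These are the only selection rules in the protocol body. None concerns body site or the likeness of one lesion to the other.

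The letters A and B then stay with the lesions throughout, but no rule says which of the two becomes A. Allocation is common to everyone: "Treatment and control will be randomized once for the entire study and all subjects based upon a one-time flip of a coin as follows".

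Section 8.1 lists three primary endpoints. Lesion size and PGA are given as changes. The third, "Visual Analog Scale of pain of injection", is not. Section 9.4 lists "Size of lesions", PGA and a pain visual analog scale (VAS). It gives no timing for the VAS and does not list body site. Section 11.1 names Kruskal-Wallis and Mann-Whitney tests as examples and no paired test. The target is 10 eligible subjects out of 12 enrolled (4.1).

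**The concern.** A within-subject comparison is efficient only to the extent that the two lesions would behave alike on the same solution. A subject with several eligible lesions could have one chosen on a finger and one on the trunk, even when a closer pair exists.

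Pain is the endpoint most exposed. A raw injection score combines the sting of the solution with the sensitivity of the site and any tenderness already present. Without a score taken just before the needle, these cannot be separated. From the second injection there is a further difficulty: if STS changes tenderness, that change is mixed with the sting.

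There is also a bias route. With one coin flip for the whole trial, the letter is the treatment. If the person choosing lesions tends to call the larger, more accessible or more prominent lesion A, that tendency falls on the same side of the contrast in every subject.

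**Working it through.** **Which endpoints are affected.** Write a lesion's outcome as subject effect + site effect + treatment effect + error. The subject effect cancels in the A minus B difference.
- *Injection pain:* a raw score, so the difference between the two site effects stays in full.
- *Size and PGA:* changes, with a lesion assessment before the first injection (9.2). A stable site effect cancels within each lesion. Only a site effect on response remains.

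**Inputs.** n = 10 comes from 4.1. The 0.05 level comes from 11.1 and is taken as two-sided, since sidedness is not stated. The documents give no SD, effect size, correlation or power, so there is no planned power figure to reproduce. The correlation rho and the true difference are assumptions.

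**Noise.** SD of a paired difference = sigma × sqrt(2(1 − rho)).
- rho = 0.3: sqrt(1.4) = 1.18 sigma
- rho = 0.6: sqrt(0.8) = 0.89 sigma
- Subjects needed for equal precision: (1 − 0.6)/(1 − 0.3) = 0.571, or 43% fewer

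Simulated power (20,000 or more runs, normal data; exact signed-rank test rejecting at W ≤ 8, Mann-Whitney at U ≤ 23):

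| True difference | Test | rho 0.3 | rho 0.6 |
|---|---|---|---|
| 1.0 sigma | Signed-rank | 65% | 87% |
| 1.0 sigma | Mann-Whitney | 52% | 53% |
| 0.8 sigma | Signed-rank | 46% | 70% |
| 0.8 sigma | Mann-Whitney | 34% | 32% |

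Over rho from 0.2 to 0.7, signed-rank power at 1.0 sigma runs from 59% to 94%. Mann-Whitney barely moves because its critical value treats the 20 scores as independent and takes no credit for the pairing.

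A second model adds site variance on top of the rest (assumed difference 1, subject variance 0.5, residual variance 0.5). If site makes up 0%, 10%, 25% or 50% of the variance of the difference, signed-rank power is 79%, 74%, 67% or 50%, and Mann-Whitney power 53%, 50%, 45% or 35%. The Mann-Whitney fall does not show what matching would recover. Matching within a subject makes the site effect common to both lesions; it does not remove site variation between subjects. The fixed-sigma table is therefore the better guide to the effect of a matching rule.

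**Bias.** Keep the second model at a 25% site share. The site variance is then 0.5/3 = 0.167 and the SD of the difference is sqrt(2 × 0.667) = 1.155. Suppose there is no treatment effect but A lesions differ systematically from B lesions by b:

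| b | Paired t rejects | Mann-Whitney rejects |
|---|---|---|
| 0 | 5% | 1% |
| 0.25 | 9% | 3% |
| 0.5 | 23% | 9% |
| 1.0 | 68% | 44% |

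The values of b are illustrative. The estimated treatment difference is shifted by b at any sample size.

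**The case against.** A reader might infer that site and tenderness distort every STS-saline contrast equally. The documents do not support that. Size and PGA are changes with a baseline assessment, so stable differences largely cancel. Nothing shows that response depends on site, or that tenderness forms part of lesion size or PGA.

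A reader might also infer that matching alone would raise power from 65% to 87%. Under the test that 11.1 names, it would not; the gain needs a paired analysis. Nor does anything in the documents show that a site rule would move the correlation from 0.3 to 0.6.

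It would go too far, too, to say that site and pre-injection pain are not collected. The Case Report Form is an attachment that was not available for review. It is listed before the injection step at the first three visits and could hold either item. Lesions are photographed at every assessment, so site may be recoverable.

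Finally, the condition is uncommon, many subjects may have only two eligible lesions, and raw injection pain is a legitimate tolerability measure. All of this limits the size of the benefit. It does not answer the central point: the rule for forming the pair and the timing of a primary endpoint belong in the protocol body, and neither is there.

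**Conclusion.** The point holds with limited scope. The protocol body has no rule that the two lesions be alike in site, does not list site as data, and describes no pre-injection pain score. The consequence is full for raw injection pain and conditional for the size and PGA changes. Because the letters are fixed by one coin flip with no rule for choosing A, a systematic selection pattern would bias the contrast; the documents do not show that such a pattern exists.

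The magnitude is illustrative. The 65% to 87% difference rests on assumed correlations, normal data, a 1.0-sigma effect and a signed-rank test. With the named Mann-Whitney test the same change gives about 52% to 53%. This is a weakness worth correcting because correction is cheap. It does not invalidate the trial.

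**What to change.** - In 9.2, add: *Where a subject has more than two eligible lesions, the two most alike in body region (mirror-image sites, or the same region and well separated) are selected before letters are assigned.*
- In 9.4 and the Case Report Form, add the body site of Lesion A and of Lesion B.
- In 11.1, compare A with B by a paired test (signed-rank). Without this, matching brings almost no gain in power.
- State when the VAS is taken, and take one for each lesion just before each injection. Use it to adjust injection pain at visit 1. At visits 2 and 3, report injection pain both raw and as change from the pre-injection score, because by then that score may already reflect treatment.

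The cost is protocol and form wording, two extra VAS marks per injection visit, and less freedom in choosing lesions. The matching rule applies only where there is a choice, so it excludes nobody. Matching reduces the room for a systematic difference between A and B but does not replace randomizing the letters within each subject, which is the direct remedy for the bias route.
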